implementation and scalability of the intervention including nurse involvement. Nurses concurred with pts experiences, and suggested strategies to recruit and retain dyads for the study, which are now included in the methodology section of the current grant proposal. Studies 3.6 and 3.7 represent the building blocks for the development of our Recovering Together program and manual. Nurses provided edits and contributed to the iterative development of the manual. These studies also confirm feasibility of conducting the pilot RCT proposed through this R21.

II. SPECIFIC AIMS

The current study has the following objectives:

Aim 1: To determine the feasibility of recruitment, feasibility of program delivery, program credibility, and program satisfaction using evidence-based benchmarks.

Hypothesis 1: We hypothesize that > 75% of the dyads approached will agree to participate.

Hypothesis 2: We hypothesize that > 75% of dyads who start the intervention will complete at least 4 sessions.

Hypothesis 3: We hypothesize that > 75% of participants will report average credibility (Credibility and Expectancy Questionnaire) scores greater than the scale's midpoint.

Hypothesis 4: We hypothesize that > 75% participants will report average satisfaction (Client Satisfaction Scale) scores greater than the scale's midpoint.

Aim 2: To demonstrate a proof of concept that the Recovering Together program can sustainably improve emotional distress [Hospital Anxiety and Depression Scale; HADS], Post Traumatic Symptoms (PTS) [PCL-S], resiliency variables (mindfulness, coping, social support and self-efficacy) and interpersonal factors (interpersonal bond).

Hypothesis 1: We hypothesize that participation in the Recovering Together Program will be associated with a more potent decrease in emotional distress and PTS compared to participation in the educational program (control), and that these improvements will maintain at 3 month follow up.

Hypothesis 2: We hypothesize that Recovering Together Program will be associated with a more potent increase in resiliency variables (mindfulness, coping, social support, self-efficacy) and interpersonal factors (interpersonal bond) compared to participation in the educational program, and that these improvements will maintain at 3 month follow up.

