For this feasibility pilot RCT, our primary outcomes (feasibility, credibility and satisfaction) will be assessed in Aim 1. Our secondary outcomes in this trial are: emotional distress, PTS, mindfulness, coping, social support, self-efficacy, and interpersonal bond, and will be assessed in Aim 2.

III. SUBJECT SELECTION

All participants will be recruited from the Massachusetts General Hospital Neuroscience ICU, using IRB approved recruitment materials.

Inclusion/Exclusion Criteria

Eligible dyads (Pts and Cgs) must meet the following inclusion criteria:

- 1) Age 18 or older
- 2) English fluency and literacy
- 3) Access to high speed internet for video sessions
- 4) Pt with an informal cg (family or friend who provides unpaid care) available and willing to participate
- 5) Hospitalized with an ANI within 1-2 weeks (pt) OR primary cg of a pt currently admitted with an ANI
- 6) Either pt or cg have clinically significant symptoms of depression, anxiety, and/or PTS

One or more of the following exclusion criteria will render a pt ineligible:

- 1) Permanent and severe cognitive impairment severe enough to impede participation – This will be determined by trained study staff through an assessment conducted as part of usual care and that includes the MMSE (score of <23) and GCS (score of <10). Nurses and study staff are trained and use these measures as part of NICU care.
- 2) Dyads where the pt is anticipated to die or to never be able to participate due to medical sequelae. This will be determined by nurses.

All adult patients and family caregivers, satisfying all inclusion criteria, are eligible for enrollment in this study regardless of sex, race, or ethnicity. Vulnerable populations will not be recruited.

Recruitment

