Patients will be recruited from the NICU at MGH from the medical team (nurses). Recruitment will be facilitated by the nursing team who will introduce the study to eligible dyads and who will also assess whether pts are able to consent, consistent with medical presentation, and cognitive status. Trained study staff will be administering the MMSE and nurses will administer the GSC, to all patients and will refer only dyads where the patients scores are higher than the established cut off scores on these measures. Consistent with NICU practice, nurses will administer the GSC. They will refer participants to the study only if they are cleared medically and cognitively. The team will page the RA using the secure Voalte system used by our team and nursing staff, when both the pt and cg are present and able to hear more about the study. The RA will only approach pts identified and cleared by the medical team. The RA will ensure eligibility of both pts and cgs based on the additional inclusionary and exclusionary criteria depicted above. The RA will finalize the screening and conduct informed consent. All participants will receive a physical copy of the informed consent form which has the contact information for the PI. If cgs cannot be reached in person in the hospital, they will be contacted via phone for screening and completion of informed consent. Cgs will be given a copy of the consent form to review while discussing the study over the telephone. We will fax or securely e-mail the consent form prior to obtaining consent. Cg will return a signed copy of the consent form. If a patient who is interested in enrolling in the study is unable to provide a full written signature due symptoms from their

ANI (unable to move or use their arm to write), then we will ask them to make their mark on the signature line in the consent form. People who cannot make their mark on the consent form can indicate consent by other means, e.g., orally, nodding their head, etc. The means by which consent was given by the subject will be documented in the consent form and research record. Patients and caregivers will be considered enrolled when they sign the consent form with the study staff. Please see details on the informed consent process in the next section, Subject Enrollment (Section IV). These procedures will be completed in a private medical space.

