The psychosocial intervention entails 6 sessions, each 30 minutes. Both the pt and cg participate in each session. The intervention is manualized, and teaches dyads resiliency (mindfulness, social support, self-efficacy, coping skills) and interpersonal communications (interpersonal bond) skills. The first 2 sessions will occur in person, during hospitalization. The next 4 sessions are chosen from 5 available, depending on each dyad's preference, and are delivered after discharge via secure live video. For the video sessions, dyads can participate from the same or different locations. During the in hospital sessions, dyads learn diaphragmatic breathing, mindfulness, self-care, and dialectics. During the video sessions, dyads learn how to identify negative thinking patterns and replace them with adaptive thoughts, how to communicate effectively and openly, how to engage in self-care, and how to accept things that can't be changed. Participants in the intervention group will also receive treatment as usual. This may include meeting with nurses, physical therapists, medical doctors, and other members of the pt's medical team. Treatment as usual may also involve administration of SSRI to those patients with motor problems.

[figure not shown]
Those in the educational program (control) will receive general health information that mimics the Recovering Together Program, but without teaching any of the resiliency or interpersonal communication skills that are hypothesized to be responsible for improvement in emotional distress. The educational program will also have 6 sessions, 2 in-person dyadic visits in the NICU and 4 dyadic virtual visits following discharge. It controls for dose and support from clinician. Both members of the dyads participate in all sessions. The topics of each session include: education about the stress of the ANI on patient and caregiver; education on the importance of self-care; education on stress associated with discharge and home adjustment; education on the importance of following up with medical recommendations; education on interpersonal stress as part of adjustment to ANI; education on self-care. The educational program condition will ensure that patients will remain blind to intervention or control and increase confidence that improvement in outcomes are due to the active ingredients of the intervention and not confounds. Participants in the educational program will continue with their

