Our primary aim focuses on trial feasibility, acceptability, credibility and preliminary effect. In pilot studies, ≥ 30 participants are recommended per group to establish feasibility and detect larger effect sizes for ≥ 1 outcome. We plan to recruit 80 dyads (160 participants), 40 dyads (80 participants) per arm to establish feasibility, acceptability, credibility and estimate effect size for emotional distress variables (primary quantitative outcomes). Assuming attrition of over 25% (in excess of what we experienced in our preliminary studies), we will have the necessary 30 dyads (60 participants) per arm. This

size is considered to yield stable estimates of M/SDs based on prior behavioral trial recommendations. Effect sizes from this study may overestimate power in future sample calculations. We chose study measures based on our theoretical frameworks, strong psychometric properties in studies of patients with ANI, and feasibility work in our prior work with ANI dyads. Feasibility will be reported as the percentage of patients enrolled in the study who complete at least 75% of the intervention sessions. Demonstration of feasibility will be assessed by the number of individuals who drop out of the study prior to completing the post- intervention assessment and the rate of missed sessions. If drop-out rate or missed-session rate exceeds 25%, revisions to the intervention may be needed. We will also report number of patients approached, enrolled, randomized and who completed time 2 and time 3 to determine feasibility.

2) Is the psychosocial skills-based intervention effective for pts and cgs in the ICU?

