[name] developed the proposed study design in collaboration with the NICU study team (nurses, physicians, clinical interns) and an MGH psychologist who specializes in using mindfulness and emotion regulation in both chronic illness and medically healthy populations. With funding from the American Heart Association, we conducted 20 qualitative interviews with pt-cg stroke dyads at risk for chronic emotional distress during NICU hospitalization. We also conducted additional clinical interviews with 10 pt-cg dyads representative of other ANI diagnoses. 83% of dyads approached agreed to participate. Pts (23) and cgs (25) were mostly women. Dyads were mostly spouses and mothers-daughter. Dyads noted interest in a resiliency program (30/30) and preferred a combination of in person and live video sessions (30/30). Dyads learned about resiliency skills (name, description, and goal) and agreed they would be helpful to them. They also noted interest in learning about: survivorship plans, adaptation to deficits (present or anticipated), and return to normal living. This led to the development and subsequent refinement (through feedback from the nursing team) of the Recovering Together Program active intervention.

3) Is the effect of the skills-based intervention for pts and cgs in the ICU durable?

We will assess feasibility, usability, and acceptability by the enrollment numbers, participants completion in at least 4 out of 6 sessions, and the questionnaires, The Credibility and Expectancy and Client Satisfaction Scale. These will be primary outcomes. The PCL-S, HADS, and resiliency measures will serve as the secondary outcomes.

We will use student's t-test to assess within-group differences in long-term outcomes. We will compare measures at the 3 month follow-up assessment to measures at the post-intervention assessment for both study arms.

We will also use t tests and chi squared tests to assess differences at the 3 month follow up.

VII. RISKS AND DISCOMFORTS

There is a risk that some participants may feel uncomfortable completing various psychological questionnaires or parts of the skills-based on intervention. Participants are free to withdraw from the study at any time, as the study is completely voluntary.

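### Session completion, a primary feasibility outcome, is defined with two cut-offs (4 or 5 of 6 sessions) and two denominators (dyads who start or patients enrolled)

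*Combined protocol and SAP*

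**What the plan says.** The combined protocol and SAP describes session completion in three places.

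- **Section II, Aim 1, Hypothesis 2:** "We hypothesize that > 75% of dyads who start the intervention will complete at least 4 sessions".
- **Section VI, question 1:** "Feasibility will be reported as the percentage of patients enrolled in the study who complete at least 75% of the intervention sessions". No pass mark is attached to this percentage and the arm is not named.
- **Section VI, question 3:** feasibility is judged by, among other things, "participants completion in at least 4 out of 6 sessions", with no denominator. The text continues: "These will be primary outcomes".

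The end of Section II also gives feasibility primary status: "our primary outcomes (feasibility, credibility and satisfaction) will be assessed in Aim 1".

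Three further statements fix the meaning of these rules. Section V: "The psychosocial intervention entails 6 sessions, each 30 minutes", and "Both the pt and cg participate in each session". Section III, Recruitment: "Patients and caregivers will be considered enrolled when they sign the consent form with the study staff". Section IV places randomisation after enrolment and the baseline assessment.

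Section VI, question 1, also sets a 25% limit on drop-out and on missed sessions, beyond which the intervention may need revision. It promises counts of patients approached, enrolled, randomised and assessed at the second and third time points. It promises neither a count of starters nor a split by arm.

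**The concern.** In a feasibility pilot, the completion rate is one of the main results, and here the analysis section disagrees both with Aim 1 and with itself.

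- **Cut-off.** A dyad that attends exactly 4 sessions is a completer under Hypothesis 2 and question 3, and a non-completer under question 1.
- **Denominator.** A patient who consents but never begins the programme counts under question 1 and is left out under Hypothesis 2. What counts as starting is not defined.

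The wording also shifts between dyads, participants and patients. Because both members attend every session together, that is mainly loose wording and is not raised as a separate conflict.

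What is at stake is the reported value of a primary outcome, and the freedom to choose the more favourable definition once attendance is known.

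**Working it through.** **The plan's own figure.** The only derived number nearby is the sample size: 30 dyads per arm after 25% attrition requires 30 / (1 − 0.25) = 40 per arm, or 80 in all. This reproduces, and it does not depend on either completion rule.

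**Cut-off.** Input: 6 sessions (Section V).

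- 0.75 × 6 = 4.5, so at least 5 whole sessions (5/6 = 83.3%).
- 4/6 = 66.7%, which is below 75%. No rounding makes the two rules agree.

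**Effect of the cut-off.** The plan gives no attendance rate, so mean attendance is an assumption, shown over a range. The value 0.75 corresponds to the plan's own 25% missed-session limit.

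Under independent attendance with probability p, the number of sessions attended is Binomial(6, p). At p = 0.75:

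- P(≥5) = 6 × 0.75⁵ × 0.25 + 0.75⁶ = 0.356 + 0.178 = 0.534
- P(≥4) = 15 × 0.75⁴ × 0.25² + 0.534 = 0.297 + 0.534 = 0.831

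To allow for dyads that attend nearly everything or drop out early, a beta-binomial was used with mean m and within-dyad correlation r, where a = m(1/r − 1) and b = (1 − m)(1/r − 1).

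Share reaching at least 4 / at least 5 of 6 sessions:

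| Mean attendance | Independent | r = 0.3 | r = 0.5 | r = 0.8 |
|---|---|---|---|---|
| 0.75 | 83.1% / 53.4% | 74.7% / 60.5% | 73.6% / 64.7% | 74.0% / 70.9% |
| 0.80 | 90.1% / 65.5% | 80.8% / 68.4% | 79.2% / 71.5% | 79.2% / 76.5% |
| 0.85 | 95.3% / 77.6% | 86.4% / 76.5% | 84.7% / 78.5% | 84.4% / 82.3% |

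Suppose the >75% benchmark of Hypothesis 2 were also applied to the question 1 percentage. The two cut-offs would then fall on opposite sides of 75% for these ranges of mean attendance:

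- independent: 0.703 to 0.839
- r = 0.3: 0.752 to 0.841
- r = 0.5: 0.763 to 0.825
- r = 0.8: 0.760 to 0.786

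**Effect of the denominator.** Enrolment is signed consent and comes before randomisation. The question 1 denominator therefore contains people who never start and, read literally, both arms. Its size cannot be worked out from the plan. A narrower comparison, within one arm of 40 randomised dyads, shows the direction. Assume 4 dyads never start and 28 complete:

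- among starters: 28/36 = 77.8% (exact 95% CI 60.8% to 89.9%)
- among randomised: 28/40 = 70.0% (exact 95% CI 53.5% to 83.4%)

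Exceeding 75% takes 28 completers out of 36, but 31 out of 40.

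**The case against.** The strongest reply is that no decision in the plan turns on the question 1 percentage. The >75% benchmark belongs to Hypothesis 2 alone; question 1 only reports a figure, and its one threshold is the 25% drop-out and missed-session limit. This is correct: the opposite-sides ranges above hold only if the benchmark is carried over. What remains is a primary outcome with two reported values.

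Second, a trial may report one rate among starters and another among those enrolled, so different denominators alone are not a contradiction. That is fair, but the plan does not present them as two rates. Question 1 says how feasibility will be reported, and question 3, in the same section, uses a different cut-off for it.

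Third, question 1 asks about the skills-based intervention, so its arm can be inferred. The context does point to Recovering Together, but a denominator of patients enrolled in the study precedes allocation and does not fit one arm.

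Fourth, the size rests on assumed attendance. At mean 0.85 both rates exceed 75% in every column; at 0.75 with clustering both fall short. This stands, and it limits the claim. So does the point that Aim 1 and question 3 already favour the 4-session rule, which makes question 1 the outlier.

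Finally, adopting the 4-session rule leaves a tension with the missed-session limit. If every dyad attended exactly 4 sessions, Hypothesis 2 would be met at 100% while 2/6 = 33.3% of sessions were missed. The two measure different things and can coexist, but readers of the results should know it.

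**Conclusion.** The concern holds. The cut-off conflict follows from the text and simple arithmetic and needs no assumption. The denominator conflict follows from the plan's definition of enrolment.

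The size depends on attendance, which the plan does not give. At means of 0.75 to 0.85, the gap between the two cut-offs is about 18 to 30 percentage points if absences are independent (95.3 − 77.6 = 17.7; 83.1 − 53.4 = 29.7). It is about 2 to 3 points at within-dyad correlation 0.8 (84.4 − 82.3 = 2.1; 74.0 − 70.9 = 3.1). A reversal around 75% is possible only over part of that range, and only if the Aim 1 benchmark is applied to both rates.

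The consequence is confined to feasibility reporting; the sample size and the 25% trigger stand. It should be fixed because the outcome is primary and the definition could otherwise be settled after the data are seen.

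**What to change.** Before outcome data are reviewed:

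1. Replace the completion sentence in Section VI, question 1, with the Aim 1 rule: dyads in which both members attend at least 4 of 6 sessions, against the >75% benchmark.
2. State the same unit and denominator in Aim 1, Hypothesis 2, and in Section VI, questions 1 and 3, and say what counts as starting.
3. Keep Hypothesis 2 on dyads who start Recovering Together. Beside it, as a supporting figure without a pass mark, report the rate among all dyads randomised to that arm, so that non-starters are visible.
4. Give an exact 95% CI for each rate; for example, 31/40 = 77.5% (61.5% to 89.2%).
5. Leave the 25% drop-out and missed-session limit and the promised participant counts as they are.

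The cost is wording and one extra percentage, which may be lower than the starters-only rate. No new data are needed, and Hypothesis 2 and the sample size are unchanged.

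### Aim 2 claims a between-arm benefit, but the effectiveness question names no analysis, no between-arm comparison is stated at post-intervention, and the one fully described test is within-arm and makes no use of baseline.

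*Combined protocol and SAP*

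**What the plan says.** Both Aim 2 hypotheses (Section II) compare the arms. Under the first, Recovering Together "will be associated with a more potent decrease in emotional distress and PTS compared to participation in the educational program (control"; under the second, it "will be associated with a more potent increase in resiliency variables" and in interpersonal bond, again relative to the educational programme. Both add that the gains will hold at 3 months. The introduction to Section VI has the measures collected at baseline, post-intervention and 3 months.

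Section VI, question 2 asks "Is the psychosocial skills-based intervention effective for pts and cgs in the ICU". The text below it describes the design collaboration, the funding, the qualitative interviews and what dyads preferred. It closes with "This led to the development and subsequent refinement (through feedback from the nursing team) of the Recovering Together Program active intervention". It gives no test, model, contrast, outcome or time point.

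Question 3 (durability) first lists outcomes, including "The PCL-S, HADS, and resiliency measures will serve as the secondary outcomes". It then describes the analysis in three sentences:

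- The first names a test and its type: "We will use student's t-test to assess within-group differences in long-term outcomes".
- The second gives the contrast for that test: in each arm separately, 3-month scores are set against those from the post-intervention visit.
- The third adds further tests at the last visit: "We will also use t tests and chi squared tests to assess differences at the 3 month follow up".

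The third sentence names neither the groups compared nor the outcomes. The only other analysis remark on outcomes is in Section IV: the time from assessment to the start of the intervention may be examined as a predictor if needed.

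**The concern.** The hypotheses are about a difference between randomised arms, first at the end of the programme and then 3 months later. The plan has a question for each part, but the first question holds no analysis. The second is answered mainly by a contrast that leaves out both baseline and the other arm.

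The practical consequence concerns the effect size. Section VI, question 1 includes preliminary effect in the primary aim, calls emotional distress the primary quantitative outcome, and sizes the trial partly to estimate its effect size. With no contrast stated, the time point (post-intervention or 3 months) and the scale (raw score, change or baseline-adjusted score) can be settled after the data are seen. The arm comparison that is implied also gives up precision that the baseline scores already offer.

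**Working it through.** **1. The plan's own figure.** Question 1 plans 40 dyads per arm and expects 30 after 25% attrition: 30 / (1 − 0.25) = 40, and 40 × 0.75 = 30. This reproduces. No alpha, power, SD, effect size or correlation is given, so there is no power statement to reproduce.

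**2. What the within-arm test measures.** Let D2 and D3 be the arm differences (intervention minus control) at post-intervention and 3 months. Let C_I and C_C be the mean changes from post-intervention to 3 months in the two arms. Among participants with both visits,

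C_I − C_C = D3 − D2.

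If an arm difference is present and maintained, D3 = D2 and it cancels. Whatever the size of D2, the within-arm contrasts then look as they would with no effect.

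A simulation shows this. Assumptions: 20,000 trials, 30 per arm, SD 1, correlation 0.5 between visits, both arms improving by 0.5 SD from baseline, two-sided alpha 0.05.

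| True arm difference, post / 3 months | Within-arm test rejects: intervention | control | Between-arm t-test at post-intervention rejects |
|---|---|---|---|
| 0 / 0 | 5.0% | 5.0% | 4.8% |
| 0.8 / 0.8 SD | 4.9% | 5.1% | 86% |

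**3. What the within-arm test does pick up.** It responds to fading. Take a 0.3 SD loss in the intervention arm with a stable control arm, 30 per arm, and dz = 0.3 / √(2(1 − r)):

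- r = 0.5: dz = 0.30, power 36%.
- r = 0.7: dz = 0.39, power 54%.

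A rejection shows change inside that arm. Without the control arm it cannot be attributed to the intervention.

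**4. What baseline adjustment adds.** Assumptions: two-sided alpha 0.05, one role at a time, true difference d = 0.6 SD, baseline–outcome correlation r. Unadjusted: noncentral t with noncentrality d√(n/2) and 2n − 2 df. Adjusted (ANCOVA): d replaced by d / √(1 − r²), one further df lost.

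| | Effective d | Power, 30 per arm | Power, 40 per arm (no attrition) |
|---|---|---|---|
| Unadjusted | 0.600 | 0.628 | 0.755 |
| r = 0.3 | 0.629 | 0.668 | 0.793 |
| r = 0.5 | 0.693 | 0.751 | 0.864 |
| r = 0.7 | 0.840 | 0.892 | 0.960 |

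The 95% CI half-width at 30 per arm is 2.00 × √(2/30) = 0.52 SD unadjusted. At r = 0.5 it is 2.00 × √(2/30) × √0.75 = 0.45 SD.

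**5. How many contrasts are open (approximate).** Section II lists seven secondary constructs. If each has one measure and patients and caregivers are analysed separately, there are about 7 × 2 roles × 2 times = 28 between-arm contrasts. About 14 of them fall at post-intervention with no stated analysis. The documents do not fix either condition: the questionnaire list in Section V does not map one-to-one onto the seven constructs, and separate analysis by role is not stated.

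**The case against.** The strongest reply has four parts.

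- **The within-arm test is asked only about durability.** Aim 2's phrase about improvements being maintained can fairly be read as maintenance within the programme arm, and 3 months against post-intervention is a recognisable answer to that. This stands as far as it goes: the test is a legitimate description. A reader might infer that the plan will compare the two within-arm p-values to claim an arm effect, but nothing in the text proposes this. Nor is the test blind to a fading effect, as the 36–54% figures show.

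- **A between-arm test is planned at 3 months.** A reader might infer that no arm comparison exists at all. The documents do not support that. The 3-month sentence follows the within-group sentence with an additive word, just after both arms are mentioned, and is most naturally between-arm. Under randomisation that comparison is valid without adjustment, so adjustment buys precision and does not remove bias.

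- **The missing contrast can be recovered.** By the identity above, D2 = D3 − (C_I − C_C) among participants with both visits, and effect sizes can be computed from arm means and SDs. This is true. What is absent is a stated estimate, interval and scale at post-intervention, so this is a gap in the plan and not an inability to estimate.

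- **It is a pilot.** Aim 2 is proof of concept, its outcomes are secondary, and the sample size follows a rule of thumb for stable means and SDs. This limits the severity. It does not remove the point, because the same section makes estimating the distress effect size one purpose of the sample.

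**Conclusion.** The point holds: it should be fixed, and it does not threaten the trial's primary purpose. Question 2 states no analysis, and no section states a between-arm comparison at post-intervention. The only fully described test does not use baseline and cannot show that an arm difference exists or lasts. The 3-month comparison is valid on its best reading, but it is unadjusted and loosely worded.

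The textual finding needs no assumptions. The size of the precision gain does: with 30 per arm, one role, d = 0.6 and two-sided alpha 0.05, adjustment raises power from 63% to between 67% and 89% for correlations of 0.3 to 0.7. None of d, alpha or the correlation is in the documents. The feasibility, credibility and satisfaction conclusions are unaffected.

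**What to change.** - **Question 2:** for each Aim 2 outcome, state the between-arm difference at post-intervention, adjusted for that outcome's baseline score, with a 95% CI.
- **Question 3:** state the same adjusted difference at 3 months and judge maintenance from it.
- **Model:** either ANCOVA at each time or a mixed model with an arm-by-time term. Fit it separately for patients and caregivers, or jointly with the within-dyad correlation modelled.
- **Within-arm change:** keep the 3-month minus post-intervention change as a descriptive estimate with a CI.
- **If the 3-month t and chi-squared tests stay:** name the two arms, the outcomes, and which test applies to which outcome.

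The cost is revised analysis wording and one standard model per outcome. No extra data, visits or participants are needed, because the baseline scores are already collected.

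### Durability rests on a within-arm difference test with no margin or interval, so apart from further improvement only a non-significant result can support it, and small or partial losses would often be missed

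*Combined protocol and SAP*

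**What the plan says.** Section II, Aim 2, Hypotheses 1 and 2 are comparative: the program is expected to outperform the educational control, "and that these improvements will maintain at 3 month follow up". Section VI, question 3 then asks: "Is the effect of the skills-based intervention for pts and cgs in the ICU durable". Its analysis has three parts.

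- The test: "We will use student's t-test to assess within-group differences in long-term outcomes".
- The contrast: "We will compare measures at the 3 month follow-up assessment to measures at the post-intervention assessment for both study arms".
- A further analysis: "We will also use t tests and chi squared tests to assess differences at the 3 month follow up". The groups to be compared are not named, and the sentence is not linked to the durability question.

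Section V places the post-intervention assessment (T2) immediately after the program and the follow-up (T3) 3 months later. On size, Section VI, question 1 states: "We plan to recruit 80 dyads (160 participants), 40 dyads (80 participants) per arm", with 30 dyads per arm expected after attrition. The plan gives no significance level, power, SD, T2–T3 correlation, tolerable loss or rule for concluding that an improvement was maintained. It does not say whether the t-test is paired.

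**The concern.** The null hypothesis of the T2–T3 test is no change, and the trial's hypothesis is also that nothing is lost. The test can reject in two directions. Worsening counts against durability and further improvement counts for it. In every other case the only result favourable to the hypothesis is non-significance, which shows neither that nothing was lost nor how much loss remains plausible. The smaller or noisier the sample, the more readily an effect would look maintained.

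There is also a mismatch of contrast. The hypothesis concerns benefit over control, but the test looks within each arm. After an acute illness, change from T2 to T3 mixes natural recovery with any fading of the program's effect, so a stable score in the intervention arm could hide a lost advantage.

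At stake is the sustained-improvement part of Aim 2, and any later trial planned on the belief that the effect lasts.

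**Working it through.** **1. The plan's own figure.** 40 dyads per arm × (1 − 0.25) = 30, which matches the stated 30 dyads per arm. With attrition above 25% it falls slightly lower (26% gives 29.6).

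**2. Assumptions.** The documents supply none of these: two-sided 5%; one role (patients or caregivers) analysed at a time, so n = 30 per arm; a paired test; equal SDs at T2 and T3; T2–T3 correlation ρ of 0.5 to 0.7.

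**3. Formula.** In units of the outcome SD, the SD of the change is √(2(1 − ρ)): 1.000 at ρ = 0.5, 0.894 at 0.6, 0.775 at 0.7. The standardised change is dz = loss / √(2(1 − ρ)). The noncentrality is dz × √30 on 29 degrees of freedom, with critical value 2.045. Example at ρ = 0.6 and a loss of 0.3 SD: dz = 0.3 / 0.894 = 0.335; noncentrality 0.335 × 5.477 = 1.84; power 0.427; miss rate 57%.

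**4. Chance of a non-significant paired T2–T3 test despite a real loss, n = 30**

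| True loss | ρ = 0.5 | ρ = 0.6 | ρ = 0.7 |
|---|---|---|---|
| 0.25 SD (half of a 0.5 SD benefit) | 74% | 68% | 60% |
| 0.3 SD | 64% | 57% | 46% |
| 0.4 SD | 44% | 34% | 22% |
| 0.5 SD | 25% | 16% | 7% |
| 0.8 SD | 1% | <1% | <1% |

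Non-significance is the likelier result only when the loss is below 0.37 SD (ρ = 0.5) or 0.29 SD (ρ = 0.7). At ρ = 0.3 the break-even loss is 0.44 SD and a 0.5 SD loss is missed 39% of the time.

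**5. What an interval would show.** The 95% half-width for the within-arm change is 2.045 × √(2(1 − ρ)) / √30: 0.37 SD at ρ = 0.5, 0.33 at 0.6, 0.29 at 0.7. A non-significant result near zero would therefore still be compatible with losing roughly 0.3 to 0.4 SD.

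**6. The between-arm contrast at 3 months, 30 per arm.** The half-width is 2.002 × √(2/30) = 0.52 SD. Power is 21% at d = 0.3, 48% at d = 0.5 and 86% at d = 0.8; 80% power needs d of about 0.74.

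**The case against.** A reader might infer that at 30 per arm a non-significant test is the likely outcome even if the whole benefit disappears. The figures do not support that. With pairing, complete loss of a 0.5 SD benefit would usually be detected, and loss of 0.8 SD almost always. The plan says its sample is aimed at larger effects. Even at 0.3 SD the miss rate drops below one half at ρ = 0.7. Pooling patients and caregivers (60 per arm, clustering ignored) would lower the break-even loss at ρ = 0.5 to 0.26 SD.

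A reader might also infer that question 3 contains nothing except the T2–T3 test. It does contain more. Since the preceding analysis is labelled within-group, the added 3-month tests are most naturally read as comparing the arms, and such a comparison could give positive evidence of lasting benefit. This stands, but only in part: the groups are unnamed, no estimate or interval is promised, and nothing says that these tests decide durability. The sentence narrows the gap without closing it.

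A third tempting step is to assume an unpaired test. On correlated data at ρ = 0.6 it would miss a 0.3 SD loss about 89% of the time, but comparing two visits within an arm ordinarily means pairing. The omission justifies asking for the word, not assuming the worse test.

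Finally, this is a feasibility pilot, Aim 2 is framed as proof of concept, and these outcomes are secondary. That limits the severity. It does not make non-significance a sound basis for a claim that the trial sets out to examine.

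**Conclusion.** The concern holds for the T2–T3 test as a basis for durability. It has no margin, interval or decision rule; apart from further improvement it can favour the hypothesis only by failing to reject; and its within-arm contrast does not match a hypothesis about benefit over control. These points need no numerical assumption.

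The size does. With 30 per arm in one role, pairing and ρ of 0.5 to 0.7, a 0.25 SD loss is missed 74% to 60% of the time and a 0.3 SD loss 64% to 46%. Full loss of a 0.5 SD benefit is missed 25% to 7%, and of a 0.8 SD benefit about 1% or less. The exposure is therefore to small losses and to partial loss of a medium benefit, not to wholesale loss of a large one. The primary feasibility outcomes are unaffected.

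**What to change.** In Section VI, question 3:

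- Name the two arms as the groups in the 3-month comparison, and make the between-arm difference at 3 months, with its 95% CI, the basis for the durability conclusion.
- Report the T2-to-T3 change in each arm as a paired estimate with a 95% CI, as supporting description only.
- State that a non-significant T2–T3 test will not be taken as evidence of maintenance, and that durability will be reported as not established when the 3-month between-arm CI includes no benefit.
- If a maintenance margin is wanted, fix it in advance in scale points. A margin taken from the observed T2 difference would be noisy at this size and meaningless if that difference were near zero or reversed. For planning, ruling out a given within-arm loss (true loss zero, one-sided 2.5%, 80% power) needs n = (√(2(1 − ρ)) × (1.96 + 0.84) / margin)². That is 88 to 53 per arm and role for 0.3 SD, and 32 to 19 for 0.5 SD, at ρ of 0.5 to 0.7.

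The cost is a rewrite of question 3, with no new visits or data. The downside is candour about precision: the between-arm interval will be about ±0.52 SD at 30 per arm, so the answer may often be that durability is not established.
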